Potential Risks

Gait Analysis

Gait analysis uses a motion capture system and force plates to estimate the forces on the muscles and skeleton during a motion under study. Motion capture uses reflective markers that are taped or glued to the skin. Tape or glue from the reflective markers could cause skin irritation. All attempts will be made to minimize the likelihood of irritation as any irritation would influence their gait abnormally and could not be sustained for long durations. Force plates may include in-ground and treadmill-integrated versions. Risks associated with gait analysis include the

possibility of falling, or of experiencing muscle strain due to exertion. We will warn subjects that minor discomfort can be normal and that they should contact us if they are experiencing unusual muscle soreness. There is additional risk of fatigue from participation in locomotion trials. These risks are similar to everyday locomotion, but subjects will be given ample time to accommodate to different conditions before formal testing.

Falls

Walking and running inherently carry some risk of falls. These risks are similar in this study to those encountered in everyday activities. There is some elevated risk due to the effects of different devices and instrumentation on device fit and function.

Device Fit

For tests with prostheses and orthoses, there is a risk of skin irritation or abrasion due to contact between the device and the limb. The fit of any devices used will be checked repeatedly throughout the experimental sessions. Subjects using prostheses will wear their daily-use prosthetic socket, or a custom version built by a certified prosthetist, in order to ensure proper fit. For take-home tests, there is a slight increase in risk of skin irritation due to the change of equipment; subjects are asked to watch for signs of such problems and contact the research team if they occur.

For some tests (for example, EMG or respiratory gas exchange measurements), the equipment itself may be uncomfortable. This equipment will be attached to the body and adjusted as comfortably as possible, and attention will be paid to subject-specific adjustments to prevent unnecessary strain or load on the body.

Device Function

Subjects may experience minor discomfort with adjusting to the different lower-limb prostheses and orthoses. This experience often passes quickly, but subjects will be instructed to inform experimenters and stop the experiment if the discomfort is too great or too persistent.

There is a risk of malfunction whenever a device is used. With lower-limb ambulatory aids (prostheses, orthoses), malfunction could result in a fall and/or muscle strain.

Electromyography (EMG)

EMG is a tool that measures muscle activity, an important component of movement control. It uses surface electrodes to measure the electrical signals produced by muscle contractions. Risks associated with this procedure are minor and may include soreness in the areas being tested. This may last for a few days and can be relieved with an over-the-counter pain reliever. Additionally, hair at the site of each EMG electrode may need to be shaved to achieve proper electrode adhesion and conductance.

Disease Transmission:

Because the same test devices, EMG equipment, pressure insoles, and respiratory gas exchange

equipment will be used by multiple subjects, there is potential for disease transmission. This risk is reduced to an extremely small level by two mechanisms. First, subjects under treatment for infectious disease will not be allowed to participate. Second, equipment surfaces with which subjects come in contact will be disinfected following each subject's use of the equipment. The manufacturers of the test equipment items provide cleaning procedures, which will be performed between subjects. For the EMG system, this includes disinfecting the electrodes. For the respiratory gas exchange system, it involved disinfecting the mouthpiece and flow meter. The experimental devices (prostheses, orthoses) will be washed and/or disinfected with a sterilizing solution, wipe or spray. For pressure insoles and footwear, this is a shoe disinfectant and/or sanitizing wipe. Clothing will be washed between uses. Subject-specific components such as the mounting straps for the FES neuro-orthoses will be purchased new for each participant.

Risk of Being Identified:

For any tests performed outside the laboratory, the subject will be in public spaces. It is possible that someone may identify the subject during study participation. This risk is elevated compared to everyday life, as any novel devices or instrumentation will be more visible than standard prostheses or orthoses.

The risk of being identified is elevated for participants whose sensors are installed off-site in a public place. Because this involves more activity including handling multiple devices and conversing about the study, there is more occasion for the use of devices and sensors to be noticed by others. This risk will be highlighted and explicitly acknowledged by the participants in the Informed Consent process.

Risk to Privacy:

In take-home studies, location tracking and reconstruction is a critical piece of the scientific approach to analyzing frequently-repeated everyday movements. This location data can potentially expose private information such as the location of home, work and other places the participant travels to. Therefore, unaltered location data will not be published as a component of a public data set. Any figures or data published will have location withheld or obfuscated (such as offsetting location by a random large distance). We will remove place names, street names and building names from figures published with subjects' location data.

One of the possible means of recording location data is through use of a cell phone app that logs data. If this approach is used, it may include an additional risk to privacy because many such apps require installation on the user's real account (e.g. Google Play or Apple Store), and additional registration with the app vendor according to the vendor's terms of use. We will inform users of this risk on the Consent form and will mitigate it as outlined below in the Minimizing Risks section.

Another risk to privacy is from audio recordings in voice recordings made during everyday life. Recordings will only be made when initiated by the participant. Users will be instructed to report

only balance- and mobility-related events using voice recordings. Precautions will be taken to ensure that the privacy of non-participants is respected, including transcription by a member of the study team who will transcribe only conversation related to the study.

Another risk to privacy is from identifiable photos/videos recorded during the procedures. Explicit permission will be sought on the Informed Consent form before identifiable images are recorded.

Minimizing Risks

Subjects will be supervised at all times during the lab and field testing and will easily be able to communicate any discomfort or fatigue. Subjects will be able to take breaks whenever necessary, and may discontinue participation at any time. Subjects will be supplied with water to drink as needed. If a treadmill is used, handrails or an overhead harness will be used to prevent falls, and emergency stop buttons will also be within reach of the subject. During balance testing on the NeuroCom Balance Master system, an overhead harness will be used. During field testing, the subject's prescribed prosthesis, orthosis, or footwear, as well as any necessary tools, will be brought along by the attending experimenter, in case the need to change or remove an experimental device arises.

For take-home testing of devices, only commercially available or standard-of-care devices will be used. Subjects will be required to self-supervise, but will be given cell phone contact information for two or more members of the study team, for contact in case any difficulty arises. Subjects will be advised to keep their prescribed prosthesis and tools available, and to check regularly for discomfort or skin breakdown. A member of the study team will make weekly calls to the participants to inquire whether there are any problems with the devices, or any adverse effects.

The "take-home" portion of the study could be affected by a pregnancy that arises after initial enrollment. Because the take-home portion only uses standard commercially available devices, the risk in this case is comparable to that of ordinary life. Nevertheless, participants will be asked if they are pregnant during each weekly call, and if so they will be asked about the estimated gestation time. Subjects will be allowed to continue or discontinue participation according to their own discretion within the first 12 weeks of pregnancy. After 12 weeks of pregnancy, participation will be discontinued.

Risk of the failure in the prostheses and orthoses will be minimized through use of devices approved for patient use. Precautions will be taken to ensure safety even if the device does fail (malfunction or break), including the following:

- During all testing, subjects will be instructed to pay attention to the feel and sound of the devices and report any changes. Experimenters will also attend to device sounds and appearance. Most failures are preceded by warning signs and can be prevented

with user attention.

- During testing on a treadmill, handrails and an emergency stop button will be available within easy reach of the subject, unless an overhead harness is used.
- During over-ground laboratory or field testing, an experimenter will follow the test subject, bringing a replacement prosthesis and tools in case the prosthesis needs to be changed.
- During running trials over-ground, the subjects will wear a helmet and knee/elbow pads.
- During running trials on the treadmill, handrails or an overhead harness will be used to prevent injurious falls.

Discomfort due to energy expenditure measurement equipment will be minimized by proper adjustment of the device to fit both the face and the torso (wearable components).

Skin irritation due to motion capture markers and muscle activity electrodes will be minimized by careful placement to avoid tugging or twisting the skin. Subjects will be instructed to report any discomfort, and the test will be discontinued if there is unresolvable serious discomfort.

Physical and psychological stress due to the physical task demands will be minimized by providing appropriate rest periods between sequential trials (ca. 5 minutes). Fatigue in lab testing will be managed by ensuring no more than 6 minutes of continuous locomotion and no more than 5 hours spent in the lab in a single day. Fatigue in field testing will be managed by accompanying the subject throughout testing. In both settings, the experimenter will regularly inquire whether the subject needs rest. Fatigue in take-home testing is expected to be similar to everyday life.

Psychological stress due to perceived performance demands will be minimized by explaining the protocol in terms of doing “what you can do comfortably” (not “the best you can”), and by reiterating that the subject can stop at any time without consequence.

Audio recordings of the subject’s voice could contain private information. The following precautions will be taken to ensure appropriate privacy protections while also ensuring the necessary data are obtained:

- Voice recordings will be made on a cell phone application only when recording is activated by the participant. Files will be transferred by the participant to the study team using a USB cable upon return to the laboratory, and will be stored with the other data files. Participants will be free to delete recordings following this transfer, but will not be required to because the files record the subjects’ own voices and events.

- Voice files will be transcribed by a member of the study team, recording only information related to the event in question (editing out background and unrelated conversation).
- Voice files will not be accessible to persons outside the study team, and only transcripts will be used for public dissemination (papers, presentations).

Identifiable photos and videos will only be recorded if consent to record and show identifiable images is given by the subjects. Non-identifiable images may be recorded for analysis and for documentation and verification of the experimental procedures even if subjects decline to give permission for identifiable images.

Risk of identification in public spaces cannot be mitigated, but subjects will be informed of this risk and can withdraw if it is unacceptable. The elevated risk of identification for those in the off-site installation procedure will be included as a dedicated item in the Consent form.

Unaltered location data (a privacy risk) will not be published as a component of a public data set. Any figures or data published will have location withheld or obfuscated (such as offsetting location by a random large distance). We will remove place names, street names and building names from any figures published with location data.

Risks to privacy derived from the need to install a cell phone app will be minimized using several different techniques, to be chosen as the sensor system is finalized. First, our preferred method is to not use a cell phone at all, but rather the fully-embedded system we are designing. If we do need an app, our preferred approach is to install a custom app that is not on the Google Play store or the Apple Store. We have developed one such app in pilot testing, and installed it directly on an iOS device (but it has limitations, and we do not yet have one for Android). If instead we choose a publicly available app (due to convenience, improved features like data transmission capability, etc.), then the need to install it on the user's own Google or Apple account cannot be avoided. In this case, we will attempt to minimize exposure of personal data to the app vendor by creating an account with lab credentials such as a lab email address (e.g. "[contact]", which will forward to a study team member instead of the subject). If none of these is practical or satisfactory to the subject, then the subject will be given the opportunity to refuse participation if he/she objects to installing and creating his/her own account.

Medical emergencies

Medical emergencies will be handled through standard emergency services (i.e., calling 9-1-1). Oversight will be provided by the PI or other Study Personnel in attendance during testing. Specific oversight of subjects who use prostheses or orthoses will be provided by the Certified Prosthetist or Orthotist, as related to limitations on activity and fitting of experimental devices

to avoid irritation or fall risk. Medical emergencies during take-home portions of the experiment will be handled by the participants without intervention by the study team. Subjects will be asked to report any emergency events to the Study Team for evaluation of whether the study contributed to the emergency.

Benefits

In the prosthetics study, subjects may receive temporary benefits from involvement in the study, if they find the test devices preferable to their prescribed devices. Such experiences could also provide information to help them improve their future care. No other benefits are expected for subjects involved in the prosthetics study. In the orthotics study, subjects benefit from the unusual circumstance of access to extended trial periods of two different foot-drop orthoses which may aid their decision making over which device to pursue. No other benefits are expected for subjects involved in the orthotics study.

There are significant potential scientific benefits in the prescription of proper prosthetic and orthotic technologies in patient care. Results from this study will provide documentation of motor behavior across a wide range of motor tasks in patients and unaffected subjects.

The proposed research will benefit society through:

- improving our understanding of how the different prostheses and orthotic interventions affect walking and running.
- improving clinical care by improving methods to assess mobility outcomes during real-world, everyday life

Data and Record Keeping

The PI will oversee the management of the study dataset. Data Confidentiality will be ensured by allowing only individuals involved with the study to have access to PHI, all identifying information, and all collected datasets, which will be stored in locked cabinets in the PI's Laboratory, on password protected computer systems, or on HIPAA compliant servers. Coding and de-identification of datasets have been described under the privacy and confidentiality section. Data collection methods have been described in detail in the study procedures section. Identifiable study records will be kept for five years after study completion at UW-Madison and de-identified data will be banked indefinitely.

Coded data with no direct identifiers will be transmitted using HIPAA-compliant means between the primary site at UW and collaborating scientists at WRNMMC. This data transmission is necessary to allow the collaborators to best analyze and interpret the data. Each site will retain the only copy of the code key for data collected at that site. Details of the data transmission have

been described in the Data Processing/Data Analysis section and the Privacy and Confidentiality section.

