To determine the comparative biomechanical benefits of different orthotic solutions to persons with drop-foot.

Tertiary objective

To perfect methods for collecting and analyzing data from wearable sensors to compare the benefits of different conditions on everyday movement.

Study Outcomes

Primary outcome

The primary outcome is biomechanical gait function, as measured through gait metrics such as limb and joint movement patterns and foot placement variability (kinematics), and joint and prosthetic socket loads and joint power production (kinetics).

Secondary outcome

The secondary outcome is behavioral gait function, as measured from preferred walking speed, stride count, breadth and perceived ease of locomotor activities, and reports of inconvenience, pain and discomfort.

Research Design and Methods

In this protocol we will perform short-term laboratory and long-term real-world locomotion testing with a variety of commercially available lower limb prostheses and commercially available orthotic solutions for drop-foot, with emphasis on using wearable sensors to compare biomechanical performance with different devices.

Subjects will perform testing inside the laboratory (“lab testing”), outside the laboratory (“field testing”) on and near the campus of UW-Madison, and/or extended testing in a home and community environment (“take-home testing”) to evaluate different aspects of device function. Lab testing may consist of standing (on one or both legs), walking (at various speeds, forward and backward), and running (from running in place to a fast jog) trials, performed on a standard treadmill, an instrumented split-belt treadmill, a moving treadmill with virtual-reality surround screen, on ramps, on stairs, and/or on the floor. Measurements will be made using standard biomechanical measurement tools such as motion capture, wearable motion sensors, force transducers, pressure insoles, electromyographic electrodes, treadmills, and respiratory gas sampling equipment. Field testing may include standing and walking trials, conducted indoors and outdoors, on level ground, uneven ground, slopes, and stairs, as well as level running. Take-home testing will consist of wearing one or more different prostheses, orthoses, or types of footwear, together with wearable sensors to evaluate their function, for periods ranging from hours to weeks of everyday life.

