Justification of Altered Consent: This study involves completing a telephone screening, questionnaires, and participating in clinical assessments and interventions that are common and currently in use in clinical practice at UW Health. These activities are similar to and of no greater risk than activities of daily living or that would be encountered during a standard clinic examination. The altered consent increases the feasibility of conducting this project (and future projects) by simplifying recruitment. These procedures also reduce the time commitment required of participants. This waiver would not adversely affect the rights and welfare of subjects.

Written Informed Consent: A copy of the informed consent document will be provided to potential participants after screening via e-mail or U.S. mail according to participants preference. Subjects will be asked to return a signed copy of written consent either via a scanned copy emailed to the study team or a signed copy sent to the study team through U.S. mail. Alternatively, subjects can provide Written Informed Consent through REDCap.

The informed consent will be cosigned prior to the start of the first data collection visit at the BADGER Laboratory. Each consented participant will be reminded that s/he may withdraw from the study at any time, for any reason, without any impact on his/her ongoing care.

Subject Compensation:

- On-site testing studies (in-lab or out-of-lab) with no take-home component:
 - Subjects in the Patient groups (users of prostheses or orthoses) will be paid \$20 per hour to compensate for their time and travel expenses.
 - Subjects in the Non-patient group will be paid \$10 per hour for laboratory sessions to compensate for time and travel expenses.
 - Subjects will be reimbursed for parking expenses (or a parking voucher will be provided).
- Long-term monitoring studies (take-home studies):
 - Subjects in the Patient groups (users of prostheses or orthoses) will be paid up to \$450 total for participation, including on-site portions:
 - Up to \$360 will be paid on a pro-rata basis based on how much of the study the subjects complete (at \$40 per week for Orthosis users, \$90 per week for Prosthesis users).
 - \$90 will be paid for completion of the full study.
 - Subjects in the Non-patient group will be paid up to \$150 total for participation, including on-site portions:

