We use standard questionnaires to rate each patient's perceived mobility and quality of life. Surveys will be administered at the beginning of the study to gauge each subject's mobility outside the lab as well as at points during the study to gauge the impact of study interventions on mobility. For subjects with Multiple Sclerosis, questionnaires will be administered for the additional purpose of assessing the impact of impairments such as fatigue on their mobility before and during the study, and to collect information on their self-rated disease severity. The specific surveys planned are the Prosthetic Limb Users Survey of Mobility (PLUS-M) [25], [26] and the Prosthetic Mobility Questionnaire [17]. Other surveys that may be considered include: MOS Short Form 36 [27]; an NIH PROMIS physical function instrument (e.g. short form 10, 11, 20) [28]; the Locomotor Capabilities Index (LCI-5) [29]; the Prosthetic Profile of the Amputee (PPA) [30]; the Prosthetic Evaluation Questionnaire – Mobility Subsection (PEQ-MS) [15]–[17]; Activities-Specific Balance Confidence scale (ABC) [31], [32]; Socket Comfort Score [33]; the Scale for Evaluation of Rehabilitation-Participation (USER-P) [34]–[36]; the Orthotics and Prosthetics Users' Survey (OPUS) [37]; the Wong-Baker faces pain rating scale [38]; and/or the PAR-PRO participation scale [39]. Some questionnaires have sections that are irrelevant to this study; these sections may be skipped when administering the questionnaires. For the MS group, additional questionnaires will include: the Modified Fatigue Impact Scale (MFIS) [40], [41], the 12-Item Multiple Sclerosis Walking Scale(MSWS-12) [42], [43], the self-Expanded Disability Status Scale (self-EDSS) [44], [45], and the Psychosocial Impact of Assistive Devices Scale (PIADS) [46].

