Finally, we will use custom questionnaires to gauge the utility of the devices under test. For the MS group, custom questionnaires will also be utilized to rate their daily fluctuations in fatigue and to communicate which shoes they utilized for the day, which is necessary as this impacts data interpretation. These questionnaires will be administered either on paper or on a computer by web form (e.g. using REDCap, Qualtrics™ or other tools compliant with HIPAA requirements). The subject code, but no other identifying information, will be collected on the form. Questions will be specific to each device or group of devices tested, because each is designed based on a different concept. Each questionnaire will be submitted for IRB review and approval prior to use with subjects.

Questions may include ratings (e.g. 0-10 ratings, visual analog scales, etc.) or rankings (e.g., best to worst, 1 to 5, etc.) of comfort, discomfort, utility, preference, pain, performance, fatigue, and specific features of the device's perceived biomechanical behavior. For example, we may ask subjects to "rate the quality of forefoot rollover movement with this prosthesis," or to "rate the severity of the mid-stance 'flat spot' you perceive with this orthosis," or "rate how comfortable would you feel relying on this device to walk along a forest trail." We will also include an optional space for open comments, because user comments provide deep insight into how these kinds of devices can be improved. The surveys will exclude sensitive questions, including but not limited to: embarrassing, damaging, personal or invasive information; information that could potentially

identify the respondent; protected health information; detailed information about any health condition or disability.

Outcome Measures

Outcomes will generally be compared using a repeated-measures design, in which each subject acts as his/her own control. This design is chosen to minimize the statistical problems caused by heterogeneity in the subject population.

- Ground Reaction Force (GRF): force applied by the body to the ground. Peak forces and shape of the force vs. time trajectory are commonly used to assess gait quality. Forces closer to “normal” are usually considered better, but this goal may not apply in persons with amputation.

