 - Before and after each take-home period, participants will come to the lab for biomechanical testing and questionnaires and to be fitted with a new prosthetic foot to use for the next period.
 - The sensor systems will be worn on the affected and/or unaffected leg and foot

and/or the waist using a dedicated strap, and/or carried in a pocket or case (e.g. for data recorded by a cell phone application) throughout the study duration.

- Prosthetics branch 2: participants with amputation will use 2 or more prosthetic feet that they already own and use regularly, with only Instrumentation (sensors) added by the study team.
 - Participants will use each prosthesis for a take-home test of 1-3 weeks of everyday life. Comparisons will include a daily-use prosthesis, a running-specific prosthesis, and any other prostheses a person uses on a regular basis.
 - The sensor systems will be worn on the affected and/or unaffected leg and foot and/or the waist using a dedicated strap, and/or carried in a pocket or case (e.g. for data recorded by a cell phone application) throughout the study duration.
 - Sensors will be installed either in the lab or at an off-site location where a team member meets the subject. In such “off-site installation” situations, a designated member of the study team will meet with the participant in a public space (possibly, but not limited to, their clinician’s office) to carry out the installation and validation of the take-home wearable sensors. The participants will then proceed with the take-home testing.
 - Only one lab or off-site installation visit is required to set up the wearable sensors. Sensors will be removed by the subject and returned through the mail, or alternatively the subject may come to the lab for the team to remove them.
- Orthotics branch: Participants with drop-foot will have a standard orthosis fitted by a certified orthotist, as well as the Bioness L300 Go FES neuro-orthosis. Other procedures are as above.
- Participants with no mobility impairment may use different kinds of footwear, including shoes, sandals, boots, and/or different insoles. Other procedures are as above.
- All subjects may participate in laboratory walking trials (treadmill or over-ground) to measure the detailed biomechanical effects of the different devices.

Instrumentation:

- Instrumentation may include any or all of the measurements listed in the *Study Procedures – General* section.

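### Nothing secures a discomfort rating when a device is stopped early, and no outcome counts early stops, so the device stopped more often could look better tolerated than it is

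*Combined protocol and SAP*

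**What the plan says.** - **Outcome.** Study Outcomes, secondary outcome: behavioral gait function, including "breadth and perceived ease of locomotor activities, and reports of inconvenience, pain and discomfort". No instrument or time point is named there.
- **Comparison.** Outcome Measures: outcomes are generally compared by repeated measures, "in which each subject acts as his/her own control".
- **Stopping.** Potential Risks, Device Function: "subjects will be instructed to inform experimenters and stop the experiment if the discomfort is too great or too persistent". The consent section adds that "s/he may withdraw from the study at any time, for any reason". Minimizing Risks advises take-home users to keep their prescribed prosthesis available.
- **Scheduled measurement.** Test Conditions, Prosthetics branch 1: "Before and after each take-home period, participants will come to the lab for biomechanical testing and questionnaires". The orthotics branch refers back to these procedures.
- **Other contacts.** Assessments, Surveys and Feedback places surveys at the start and "at points during the study to gauge the impact of study interventions on mobility", with no dates. Minimizing Risks provides weekly calls about device problems and adverse effects. The consent and privacy sections have most questionnaires completed online through REDCap.
- **Analysis.** Data Processing/Data Analysis names repeated-measures ANOVA for EMG, kinematic, kinetic and metabolic data. It names no model for the discomfort reports and no rule for a missing device condition.

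**The concern.** Stopping a device because it hurts is itself a result on the tolerability outcome, and probably the most informative one. The plan foresees such stops but makes no provision for measuring them. The score that would reflect everyday wear is scheduled for the visit after the period. The visit before the period is when the new foot is fitted, so a rating then cannot show discomfort that develops or persists in use.

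If a person who stops has no later score on that device, a paired analysis has no contrast to use. The comparison is then made among people who tolerated both devices. When one device is stopped more often, its worst experiences are the ones removed. This goes beyond a missing analysis detail, because a rating that was not taken at the stop cannot be recovered later by the analyst.

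At stake is whether the comparison of pain, discomfort, inconvenience and ease can support prescription, which is the evidence gap the Background sets out to close.

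**Working it through.** **1. The plan's own figure.** The Sample size section uses N = 2 × ((1.96 + 0.84) × σ/d)².
- Ankle push-off: 2 × (2.80 × 1.5/3.1)² = 3.67, rounded up to 4.
- Opposite-leg collision work: 2 × (2.80 × 0.04/0.055)² = 8.29, rounded up to 9.

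Both match the stated 4 and 9. They concern other outcomes and are not affected by this point. The planned 10 per test is the only figure carried forward.

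**2. Is an early stop captured?** The outcome lists (Study Outcomes, Outcome Measures, and the Intended Outcomes under Specific Procedures) contain no item for a device period ended early. The weekly calls sit under risk minimisation and are not named as outcome data. The surveys during the study have no schedule, so none is guaranteed before or at a stop.

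**3. Size if people who stop are left out (all inputs assumed).** Take discomfort scores on devices A and B as bivariate normal, in units of the SD of one device's score, with within-person correlation ρ. The share q with the worst scores on A stop A, have no score on it, and leave the paired comparison. Nobody stops B. With c the (1 − q) normal quantile and φ the normal density:

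bias in the mean A − B difference = −(1 − ρ) × φ(c)/(1 − q)

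| q | c | φ(c)/(1 − q) | Understated, ρ = 0.3 | ρ = 0.5 | ρ = 0.7 |
|---|---|---|---|---|---|
| 10% | 1.282 | 0.195 | 0.136 SD | 0.097 SD | 0.058 SD |
| 20% | 0.842 | 0.350 | 0.245 SD | 0.175 SD | 0.105 SD |
| 30% | 0.524 | 0.497 | 0.348 SD | 0.248 SD | 0.149 SD |

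At ρ = 0.5, a true excess of 0.50 SD on A appears in simulation as 0.40, 0.32 or 0.25 SD, with about 9, 8 or 7 of 10 pairs left.

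**4. Stops on both devices (simulated, ρ = 0.5, true excess 0.50 SD).**
- 20% stop A and 5% stop B: 0.37 SD is shown.
- 20% stop each: 0.50 SD is shown, so the bias is about zero.

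**5. One common stopping threshold.** Assume mean scores of 4 (A) and 3 (B), SD 2, ρ = 0.5, and the same threshold for both devices. The true difference is 1.00.
- Threshold 6: 15.9% stop A, 6.7% stop B; completers show 0.83, which is (1.00 − 0.83)/2 ≈ 0.08 SD lost.
- Threshold 7: 6.7% and 2.3%; completers show 0.91, about 0.04 SD lost.
- Threshold 8: 2.3% and 0.6%; completers show 0.96, about 0.02 SD lost.

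**6. Would a worst-rank test be a safe main analysis?** For 10 pairs, the exact two-sided signed-rank test needs the smaller rank sum to be 8 or less (p = 0.049 at 8, 0.064 at 9). If one person stops A and another stops B, the two largest ranks, 9 and 10, fall on opposite sides. Each rank sum is then at least 9, so p cannot fall below 0.064 whatever the other eight people report.

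**The case against.** The strongest reply is that the plan leaves early stops unaddressed but does not mishandle them.

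- **Timing.** A reader might infer that scores exist only at the end of a period. The documents do not support that. Questionnaires also come before each period, surveys may fall during the study, and REDCap allows a rating at any time. This stands, but none of these routes ensures a rating at a stop.
- **Exclusion.** A reader might infer that people who stop are dropped. The plan neither says so nor bars a rating after stopping, and ANOVA is not named for discomfort reports. Those reports could also come from weekly calls or voice recordings. This stands: exclusion is a condition of the argument and not a fact about the plan.
- **Direction.** A reader might infer that the bias always favours the abandoned device. It does so only if stopping is unequal, as step 4 of the working shows.
- **The stop instruction.** It does not say whether the experiment means a session, a device period or the whole study. It cannot be read simply as giving up a take-home device.
- **Selection at entry.** Multiple Sclerosis participants must be able to wear both devices comfortably, which may make stops rarer in that group.
- **Weight.** Discomfort is one component of a secondary outcome, and the secondary outcomes under Specific Procedures list only gait measures. That limits the importance of the point without removing it.

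**Conclusion.** The concern holds in conditional form. The plan compares pain, discomfort, inconvenience and ease within person and foresees that people may stop for discomfort. It neither secures a rating at that moment nor counts the stop. If people who stop have no later score and are left out, and one device is stopped more often, that device will look better tolerated than it is.

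The documents give no stopping rates, so any size is illustrative. With 10-30% stopping one device only and a correlation of 0.3-0.7, the understatement is about 0.06-0.35 SD. It is smaller when some people also stop the other device, and about zero when stopping is equal.

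A reader might infer that half or more of the difference is lost. For example, suppose one of 10 people stops with a difference of 5 points while completers average 0.5. The all-person mean is (9 × 0.5 + 5)/10 = 0.95, against 0.5 in completers. That result follows from the assumed 5 points and from placing the stop on one device. Nothing in the documents supports either input.

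**What to change.** 1. Add to the secondary outcome an item for a device period stopped early or the participant's own device resumed, with date and reason, and report it by device.
2. Take the pain, discomfort, inconvenience and ease ratings at the time of stopping, through the existing weekly call or a REDCap link, and use them in the within-person comparison.
3. Show the completer-only results beside this.
4. Keep a worst-rank analysis as a sensitivity analysis only. State that with about 10 people it cannot reach p < 0.05 if one person stops each of two devices, so it can lose all power when stops occur on both.
5. Clarify whether the instruction to stop the experiment refers to a session, a device period or the whole study.

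None of this changes when a participant stops. The cost is a few lines of text, one question on a call already planned, one short form and a small extra analysis. One limitation should be stated in the report: a rating taken at a stop reflects less wear than an end-of-period rating. That is why both sets of results are shown.
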